**A. PURPOSE OF THE STUDY:**

Determine if an interactive virtual reality (VR) intervention will decrease post-sedation negative behavioral changes one week after ED (emergency department) sedation.

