**B. SPECIFIC AIMS/HYPOTHESES**

- 1) Specific Aim: To determine whether a non-pharmacological virtual reality intervention (non-invasive, technology-based distraction via interactive digital game participation) will decrease the incidence of post-sedation negative behavioral changes in children undergoing procedural sedation with IV ketamine in the pediatric ED following their discharge home.
  - i. Hypothesis: Fewer children in the intervention group will have post-sedation negative behavioral changes at 1 week follow up post-discharge as compared to the control group who receive standard of care.
- 2) Secondary Aim: To determine whether administration of a non-pharmacologic virtual reality intervention will decrease anxiety levels just prior to procedural sedation.
  - i. Hypothesis: Children in the virtual reality intervention group will have less anxiety just prior to procedural sedation when compared to controls as evidenced by a reduction in their Modified Yale Preoperative Anxiety Scale (m-YPAS).

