- Demographic Data: The research assistant (or other member of the research team) will collect routine demographic data from the electronic medical record and/or from the patient's parent or guardian including age in years, gender, race, weight in kilograms, medical comorbidities, procedure type and history of sedation difficulty. Additionally, the parent/guardian will be asked to provide their phone number and select the best time of day for the research assistant (or other member of the research team) to call for phone follow-up, cell phone number to text, provide an email address, and mailing address. Parents will be contacted by the research assistant (or other member of the research team) at 1 week follow up via phone, text, email (via secured REDCap link) and/or mail to complete the post-hospitalization behavior questionnaire (PHBQ) and pain survey. One PHBQ survey and pain survey is completed. This information will be collected by the Research Assistants (or other member of the research team) on questionnaires on REDCap or by paper. See Appendix C.
- Measures:
  - Anxiety: To assess the patient's anxiety, the following assessment tool will be used.
    - Modified-Yale Pediatric Anxiety Score (m-YPAS): See Appendix D.

The m-YPAS is a widely used by medical providers to assess patient anxiety at the time of induction of anesthesia. It is designed to be completed in less than 1 minute. It was originally developed for use in children ages 2-6 years but has since been modified to include adolescents. It is reliable and its validity compares favorably to that of the gold standard, the STAI-C (Kain, Z. 1997). The patient's provider (attending physician or fellow physician) will assess the patient's anxiety using the m-YPAS twice during our study: 1st upon patient arrival and enrollment and 2nd immediately preceding sedation after VR intervention or standard of care (depending on which group patient has been randomized to). This will be given to the research assistant (or other member of the research team) to score. The score will not be shared with the physician.

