At the closure of the game the research assistant (or other member of the research team) will remove the headset. The headset will then be thoroughly cleaned with hydrogen peroxide wipes and/or replacement of facemask according to standard infection control recommendations for the CHARIOT VR device before the next study participant's use. See Appendix J.

After intervention and immediately preceding sedation, anxiety measures using m-YPAS will be reassessed by the medical provider (attending physician or fellow physician).

The physician will perform the sedation per CHW ED sedation policy. The sedation will be administered and as appropriate the patient discharged. Child life consultation by nursing staff or medical provider as an adjunct to patient care during ED course will be permitted per standard procedure and noted. See Appendix K.

Follow-up with the family will be performed by the research assistants (or other member of the research team) between 7-14 days after ED discharge consistent the procedures followed previously (Pearce et al., 2017). Phone, secured REDCap email/text, and mail surveys will be sent. One PHBQ and pain survey will complete the study. Follow up contact via email/text will include instructions for the parent to complete the PHBQ survey and pain questions via a link that will be provided through the secured REDCap database and record their responses electronically. Script content will be consistent with the example documented in Appendix L. The phone follow-up attempts will take place during the hours agreed upon by the parent(s)/guardian(s). The phone follow-up attempts will occur no more than two times per day during the follow-up period. During the phone, email, text or mail follow-up, the PHBQ post-sedation will be administered to assess the degree of change PONB changes post-sedation as well as 3 additional questions regarding post-discharge pain treatment: (1) Was your child prescribed an opiate medication (ie. oxycodone) prescription for pain control at home? (2) Did you fill this prescription? (3) Have you given your child an opiate medication for the pain following discharge from the ED? This phone survey was utilized in a prior study and took no longer than 5 minutes to complete. If the parent(s)/guardian(s) are not reachable by phone after the period specified above, then a paper copy of the follow-up survey will be mailed to him/her along with a self-addressed stamped envelope for return of the survey.

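### The fallback rule posts the paper PHBQ only after the 7-14 day follow-up period, so those forms miss the window for the 1-week primary outcome, and other sentences place mail inside it

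*Combined protocol and SAP*

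**What the plan says.** All references are to the combined protocol and SAP.

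- **Time point.** Section A asks whether the intervention will "decrease post-sedation negative behavioral changes one week after ED (emergency department) sedation". The hypothesis in Section B concerns "post-sedation negative behavioral changes at 1 week follow up post-discharge".
- **Working window.** Section D (follow-up paragraph of the study procedures) has families contacted "between 7-14 days after ED discharge consistent the procedures followed previously". Phone attempts are limited to two a day during the follow-up period.
- **Mail as a mode within follow-up.** The Demographic Data item of Section D has parents contacted "at 1 week follow up via phone, text, email (via secured REDCap link) and/or mail". The follow-up paragraph, just after setting the window, states: "Phone, secured REDCap email/text, and mail surveys will be sent".
- **Mail as a fallback.** The same paragraph ends with the rule that if parents "are not reachable by phone after the period specified above, then a paper copy of the follow-up survey will be mailed to him/her".
- **Analysis.** Section O compares proportions by chi-square or Fisher's exact test, with a covariate-adjusted logistic regression. Its missing-data text assumes missing at random and imputes items. It gives no latest date for a valid PHBQ and no rule for a form completed after day 14.

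**The concern.** A form posted after day 14, with postal time both ways, cannot describe the child within the protocol's own window. Parents answering then may report on a later state. If negative behaviours have partly resolved, event rates fall in both arms and the absolute difference shrinks, so the 1-week result becomes a mixture of time points.

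Staff also cannot tell from the text whether paper goes out around day 7 or after day 14. With no cut-off and no handling rule, whether a form completed in, say, week 4 counts as the 1-week outcome would be decided after the data are in. Parents stay at the bedside during the VR game, so they know the allocation when they report the outcome; that is a poor setting for a post hoc choice.

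**Working it through.** **1. The sentences side by side.** Before the fallback sentence, the paragraph gives one follow-up period: 7 to 14 days after discharge. The only other timing detail is the hours of the day agreed for calls, which is not a period after which a parent could be declared unreachable. So the fallback posts paper after day 14. The two other mail sentences put mail inside the 1-week follow-up. Both cannot describe the same mailing. If there are two mailings, the text does not say so.

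**2. The plan's own sample size.** Inputs from Section E: 25% versus 10%, significance level 0.05 (two-sided assumed, as sidedness is not stated), 80% power, 20% dropout. With unpooled variance:

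n = (1.960 + 0.842)² × (0.25 × 0.75 + 0.10 × 0.90) / 0.15² = 96.8, so 97 per arm; 2 × 97 / 0.80 = 242.5, so 243.

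Both figures reproduce. Exact chi-square power at 97 per arm, summing the binomial probabilities of all tables with |z| > 1.96, is 80.2%. There is almost no reserve.

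**3. Effect of late forms that are kept.** The documents give neither the share f of late forms nor the ratio r of late to 1-week event rates. Both are assumptions, taken as equal in the two arms. Each rate is multiplied by 1 − f(1 − r).

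| f | r | Multiplier | Control | VR | Difference (points) | Exact power |
|---|---|---|---|---|---|---|
| any | 1.00 | 1.000 | 25.0% | 10.0% | 15.0 | 80.2% |
| 10% | 0.75 | 0.975 | 24.4% | 9.8% | 14.6 | 79.0% |
| 10% | 0.50 | 0.950 | 23.8% | 9.5% | 14.3 | 77.7% |
| 10% | 0.25 | 0.925 | 23.1% | 9.3% | 13.9 | 76.3% |
| 30% | 0.75 | 0.925 | 23.1% | 9.3% | 13.9 | 76.3% |
| 30% | 0.50 | 0.850 | 21.3% | 8.5% | 12.8 | 72.1% |
| 30% | 0.25 | 0.775 | 19.4% | 7.8% | 11.6 | 67.4% |

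**4. Effect of excluding late forms instead.** At 10% late, 97 × 0.9 leaves 87 per arm and power 75.1%. At 30% late, 97 × 0.7 leaves 68 per arm and power 64.6%. Keeping the forms gives more power in every row above (76.3-79.0% and 67.4-76.3%). The order reverses if the difference vanishes after day 14. With late rates of 10% in both arms, the control rate becomes 0.9 × 25% + 0.1 × 10% = 23.5%, or 0.7 × 25% + 0.3 × 10% = 20.5%. Against 10%, power is then 72.7% or 53.8%, below the 75.1% and 64.6% from exclusion.

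**5. What bias between arms would take.** Suppose 30% of control forms and 10% of VR forms are late, with r = 0.50. The rates become 25% × 0.85 = 21.3% and 10% × 0.95 = 9.5%, a difference of 11.8 points with power of about 63%. With no true effect and 25% in both arms, the same imbalance gives 21.3% versus 23.8%, a false difference of 2.5 points. Nothing in the documents suggests such an imbalance.

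**The case against.** The strongest case on the other side has four parts.

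- **Mail is not only late.** A reader might infer that paper is sent only after the window and that every mailed primary outcome is therefore late. The two other mail sentences in Section D contradict that. The point covers only forms sent under the fallback rule. This objection stands, but it leaves a conflict to resolve.
- **Fading is assumed.** The background in Section C describes negative changes that persist for weeks to months, which sits badly with event rates dropping sharply soon after day 14. At r = 1 nothing is lost, and the mildest row costs about 1 point of power. This stands, so the power figures illustrate a risk and do not demonstrate harm.
- **The late share may be small.** The fallback applies to parents not reached by phone, who also have email and text routes. The 97 per arm is already net of 20% dropout, so 30% late among those 97 means 0.20 + 0.80 × 0.30 = 44% of enrolled families without an in-window reply (28% at 10% late). Families recovered late could also come out of the dropout allowance and add to the 97. This stands; the 30% rows are an upper end.
- **A last attempt by post is ordinary retention practice, and a late form can be worth more than none.** True, and step 4 supports keeping such forms unless the effect has disappeared. It does not defend the timing, because the same form posted earlier can come back inside the window.

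**Conclusion.** The point holds for forms sent under the fallback rule. Read naturally, that rule places them outside the 7-14 day window for the 1-week primary outcome. It conflicts with the sentences that use mail within the window, and Section O has no rule for late forms. These facts rest on the text alone.

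The size is conditional. With 10-30% late forms and late rates at 25-75% of the 1-week rates, equal in both arms, power falls from 80.2% to between 79% and 67%; with no fading the loss is zero. A reader might also infer that the rule biases the comparison. The documents do not support that: the rule is the same in both arms, and bias would need late return or fading to differ by arm. Equal dilution shrinks a true difference but does not create one. Nor does the point justify limiting the primary analysis to in-window forms, which costs more power than keeping late forms in every scenario tabulated.

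**What to change.** - Make the mail sentences in Section D (Demographic Data and the follow-up paragraph) agree on when paper is sent.
- Post the paper form within the window, either with the first electronic contact or at the first failed contact, about days 7-8.
- Record the completion date and mode of every PHBQ. Section J has paper destroyed after data entry, so the completion date must be entered in the database first.
- In Section O, keep forms completed after day 14 in the primary analysis, flagged, and pre-specify a sensitivity analysis limited to forms completed on days 7-14. Report the number of late forms by arm, so that any imbalance can be seen.

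The cost is protocol wording, postage for some families who would have replied electronically, and one extra analysis. Earlier posting will not remove all late returns, which is why the handling rule is needed as well.

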**E. TOTAL NUMBER OF HUMAN RESEARCH PARTICIPANTS PROPOSED FOR**

## **THIS STUDY AT THIS SITE AND GLOBALLY. WHAT ARE THESE NUMBERS BASED ON?**

We will require 243 child subjects in the study. Allowing for a 20% dropout, we will have 97 subjects in each group. This will give us at least 80% power at a significance level of 0.05 to detect a difference of 15% (25% in the control group and 10% in the experimental group) in the proportion of patients with post-sedation negative behavioral change. This change was deemed a clinically relevant change by pediatric emergency medicine physicians.

### **F. DRUGS OR PROCEDURES**

See appendices A-K.

### **G. RISK CATEGORY:**

(1) [45 CFR 46.404](#) - Research not involving greater than minimal risk to the children.

### **H. RISKS AND THE PRECAUTIONS WHICH WILL BE TAKEN TO MINIMIZE RISK EXPOSURE**

This research does not involve greater than minimal risk to children. The only risks to patients and their families are the 30-minutes required to complete the surveys, potential risk for nausea/dizziness or headache, the 5-minutes for follow-up contact (via phone call, secured REDCap email, text, or mail), and the risk of confidentiality outlined below. Patients with preexisting nausea, vomiting, dizziness, or a history of motion sickness are excluded from participation in the study. We expect a 2.5% or lower incidence of intolerability (primarily nausea and dizziness), in which case the VR headset can simply be removed and any follow up care can be assessed by the patient's medical provider (Aminabadi et al., 2012, Wismeijer and Vingerhoets, 2005, Gold et al. 2006). Treatment for the low but potential risk of dizziness and/or nausea is primarily to remove the device, as consistent with other studies. Medical providers will evaluate patient at bedside and determine if further intervention, such as an anti-emetic is indicated. The study does not cover the cost of nausea medication, should it be required. This is clearly explained in the consent/assent documentation for review prior to participation.

Per recommendations of the IRB administrative offices, VR, being implemented as a distraction tool in the form of an interactive game prior to sedation for pediatric patients in the Emergency Department, is considered a medical device. We are submitting the FDA form regarding the use of a device in a study because this is being considered a "medical device" at CHW due to the following description, "it is ...intended for use in the potential mitigation of anxiety , in man, or other animals." The use of the device is hypothesized to reduce (mitigate) post-sedation negative behavior changes and pre-sedation anxiety as measured by PHBQ and m-YPAS scores, respectively. We contend that the device while viewed this way is at least a non-significant risk (NSR) device and can be ruled on by the IRB.

### **I. PROVISION FOR THE PROTECTION OF PRIVACY OF SUBJECTS AND TO MAINTAIN THE CONFIDENTIALITY OF DATA**

Study data will be collected and managed using REDCap electronic data capture tools hosted at the Medical College of Wisconsin. REDCap (Research Electronic Data Capture) is a secure, web-based application designed to support data capture for research studies, providing: 1) an intuitive interface for validated data entry; 2) audit trails for tracking data manipulation and export procedures; 3) automated export procedures for seamless data downloads to common statistical packages; and 4) procedures for importing data from external sources.

### **J. PROVISIONS FOR MONITORING DATA TO ENSURE THE SAFETY OF SUBJECTS; AND ADDITIONAL SAFEGUARDS TO PROTECT THE RIGHTS AND WELFARE OF SUBJECTS WHO ARE LIKELY TO BE VULNERABLE**

Each medical record number (MRN) will be assigned a study ID number. The study ID number will be used to identify all data. There will be one computer file that links the study ID and the MRN. This file will be locked and kept separately from the database. All data entered on paper forms will be labeled with the study ID. The data will be entered by a trained research assistant (or other member of the research team) into the database and then the paper will be destroyed.

**K. ANTICIPATED BENEFITS ASSOCIATED WITH THE PROTOCOL TO HUMAN RESEARCH PARTICIPANTS AND SOCIETY**

Participants may benefit from the use of an interactive virtual reality intervention prior to procedural sedation, but this is not guaranteed. Virtual reality is a safe technology, and it has been well-tolerated by most participants in a variety of different disciplines. Researchers have used virtual reality headset and activities to relieve pain and anxiety associated with dental procedures. For instance, Aminabadi et al. showed decrease pain during dental procedures in children ages 4-6, and only 3 of the 130 healthy children failed to complete the virtual reality treatment. Similarly, Wismeijer and Vingerhoet examined ten studies that utilized virtual reality to improve conditions in patients with phobias and panic disorders. Their research showed a significant analgesic effect using virtual reality when it was compared to the controls in the studies investigated, and very few negative side effects were reported. This study rated nausea and the side effect to the virtual reality intervention as negligible to nonexistent (Wismeijer and Wingerhoet, 2005)

Several other studies have also reported low or no side effects from the use of a virtual reality intervention in children. Parson et al. used virtual reality in children to study attention performance in children with attention deficit-hyperactivity disorder. None of the participants experience simulator sickness. In addition, virtual reality reduced chronic pain and no discomfort due to the headset was reported (Jones et al., 2016 ). Only one patient experienced nausea out of thirty and none of the patients dropped out of the study. Mosso-Vazquez et al. reported 3 of the 67 patients experiences nausea and vertigo which interfered with the cybertherapy to determine whether virtual reality decreases pain during cardiac surgery. During research involving Autism spectrum disorder patients experienced a low level of negative effects using virtual reality headsets (Newbutt et al., 2016). Children in a pilot study aged 10- 17 received virtual reality cybertherapy during painful cancer chemotherapy. All 11 patients responded that chemotherapy using virtual reality was better than previous chemotherapy treatment (Schneider and Workman 2000). All participants completed the study and would like to use the virtual reality head set for future studies.

Very few investigations involving children and virtual reality in emergency departments have been reported. Das et al. compared teaching residents procedural sedation using the traditional web-based educational module to a virtual reality environment. Students performed similarly although the virtual environment was reported to be more enjoyable (Das et al., 2016).

Since virtually reality can allow users safe, repeatable and a different intervention each time, it can be beneficial to typically developing children and also children with disabilities (Parson et al., 2017). Evidence indicates children do not experience more negative effects with virtual reality headset than they experience with other screen-based media (Parsons et al, 2007, Peli et al.,1998). Participants can immediately withdraw from the study at any point.

There is potential benefit to the public in greater understanding of sedation for the pediatric patient, potentially resulting in improved patient care, satisfaction, outcome and a less stressful medical environment.

**L. STOPPING POINTS THAT WOULD NOT ALLOW THE STUDY TO CONTINUE AS PROPOSED**

N/A

**M. IS THERE A DATA SAFETY MONITORING BOARD IN PLACE? WHO ARE IT'S MEMBERS? HOW OFTEN DO THEY MEET?**

N/A

**N. DESCRIBE HOW THE CONSENT PROCESS WILL TAKE PLACE. INCLUDE A LIST OF APPROPRIATELY TRAINED PERSONNEL WHO WILL BE INVOLVED.**

Patients will be identified by trained research assistants (or other member of the research team). Enrollment criteria will be reviewed and consent and assent obtained. Parental/guardian consent will be obtained for all patients. A separate assent form will be completed for patients aged 7 to 13 years. See attached consent and assent forms.

**O. PROCEDURES TO BE EMPLOYED IN ANALYZING DATA AND THE ANTICIPATED SIGNIFICANCE OF THE PROPOSED STUDY.**

- Missing data handling: Every effort will be made to avoid missing data. Using logistic regression, the assumption of missing at random (MAR) will be explored. In general, we will assume MAR, and multiple imputations will be used for items.
- Patient demographic and characteristics data: To evaluate comparability between treatment groups regarding patient demographic and baseline characteristics, descriptive statistics such as mean, median, standard deviation, range, frequency will be used to summarize the data. To compare the two groups, a student's t-test will be used for continuous variables. Where necessary, for parametric assumption, we will employ appropriate transformations with justifications. If data cannot be appropriately transformed, we will compare continuous variables between the two groups using a Mann-Whitney test. A chi-square or Fisher's exact test will be used for categorical variables.
- Analyses for Specific Aim #1: A chi-square or Fisher's exact test will be used to compare the proportion of negative behavioral change between two groups. Logistic regression analysis will be performed to compare the proportions after adjusting for covariates.
- Analyses for Specific Aim #2: The change of anxiety scores will be compared between two groups using a student's t-test or a Mann-Whitney test if the parametric assumption is not met and the data cannot be appropriately transformed. A generalized linear model will be used to compare the change of anxiety scores after adjusting for covariates.
- Statistical software SAS version 9.4 will be used for the analyses and a p-value < 0.05 will be considered as statistically significant.

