#### **D. DESIGN AND METHODS**

[figure not shown]
- Study Design: This is a randomized control trial.
- Site: Children's Hospital of Wisconsin (CHW) ED.
- Subjects: Subjects will be recruited during ED hours when research assistants (or other member of the research team) are available.
  - Inclusion criteria: Children ages 6 years to 17.5 years old receiving procedural sedation with IV ketamine in the CHW ED for long bone fracture reduction. See Appendix A. This age group is most likely to achieve positive effects, fit the VR headset equipment, and tolerate the device without adverse side effects.
  - Exclusion criteria: Patients with moderate to severe developmental delay will be excluded because the anxiety scoring tools have not been validated in this population. Non-English-speaking patients/families will be excluded because the parent survey questionnaire has not been developed and validated in languages other than English. Patients taking psychotropic medications will be excluded because these pharmaceuticals may affect measuring the primary outcome, PONB changes. See Appendix B. Patients with a history of severe motion sickness will be excluded. Patients currently experiencing nausea will be excluded. Patients who have severe visual impairment will be excluded as the VR intervention engages patients in an interactive game that requires navigation through visual content on the VR headset/screen. Patients with an expected admission to the hospital post-procedure will be excluded because outcome data may be affected by this. For a portion of patients this will not be known until after the fact. These patients will be excluded and considered screening failures.

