- **Procedure Measures:** Variables that might be associated with the primary outcome will be collected. Following the procedure, charts will be reviewed to collect: 1) the type of pain medication given in the ED, 2) the dose (mg/kg and total number of doses) of pain medication given in the ED, 3) the anxiolytic medication given in the ED, 4) the dose (mg/kg and total number of doses) of anxiolytic medication given in the ED, 5) the type of pain medication prescribed for home, and 6) the dose (mg/kg and total number of doses) of pain medication prescribed for home. See Appendices E and F.
- **Outcome Measures:**
  - **Post-Hospitalization Behavior Questionnaire (PHBQ):** See Appendix F. The PHBQ is a parent-report questionnaire with 27 items in six categories, comprising general anxiety, separation anxiety, sleep anxiety, eating disturbance, aggression towards authority, apathy, and withdrawal. This questionnaire has been used extensively since its development in 1966 to study negative behavioral changes in children post-surgery or hospitalization (Kain et al., 1996, Kain et al., 1999) and was recently used to evaluate the same after minor ED procedures (Brodzinski et al., 2013). This questionnaire takes approximately 10 minutes to finish. This tool will be completed by a parent(s)/guardian(s) prior to the sedation and during phone or mail follow-up post-sedation.

Procedures of the study: The study procedure is outlined in the diagram below (Figure 1).

Figure 1. Procedures of the study

Patients will be identified by trained research assistants (or other member of the research team) and enrollment criteria will be reviewed. Parent/guardian consent will be obtained for all eligible patients. A separate assent form will be completed for patient's aged 7- 13 years. Demographic information will be collected from the parent/guardian.

Patient's anxiety measures using the m-YPAS will be completed at baseline by the patient's medical provider (attending physician or fellow physician). A PHBQ will be completed at baseline by the patient's parent. Patients will then be stratified into high and low anxiety groups based on their baseline m-YPAS score (score of 40 or greater being highly anxious) (Pearce, et al., 2017, Kim, et al., 2012, Kain, et al., 2006) and randomized in blocks of 4 by a computer to either the control or experimental group on a 1:1 ratio. See Figure 1.

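### Aim 2 lists an unadjusted test of m-YPAS change, then a model with unnamed covariates, and does not say which decides; a named model with baseline and stratum should lead

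*Combined protocol and SAP*

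**What the plan says.** Section O gives two analyses for Specific Aim 2. The first is unadjusted: "The change of anxiety scores will be compared between two groups using a student's t-test or a Mann-Whitney test", with the rank test used if the parametric assumption fails and no transformation helps. The second is adjusted: "A generalized linear model will be used to compare the change of anxiety scores after adjusting for covariates". No covariate, distribution or link is named, and neither analysis is called the main one.

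Section D describes the design. The baseline score is planned for every child ("Patient's anxiety measures using the m-YPAS will be completed at baseline"), and it determines the randomisation stratum: "Patients will then be stratified into high and low anxiety groups based on their baseline m-YPAS score". The cut is at 40, with blocks of 4 and 1:1 allocation. The second score is also taken in the ED: "After intervention and immediately preceding sedation, anxiety measures using m-YPAS will be reassessed by the medical provider".

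Nothing elsewhere supplies the covariates. The medication variables in Section D are tied to the primary outcome and assigned to no model. The time from headset removal to the second score exists only in the VR arm, so it cannot be a covariate in a comparison between arms.

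**The concern.** The trial stratifies randomisation on the baseline of the same score that Aim 2 analyses. Stratification makes the arms more alike at baseline than chance would. A two-sample test of change without the stratum or the baseline as a covariate does not know this, so it reports more uncertainty than the design leaves. Subtracting the baseline also fixes its slope at 1, which is efficient only if the true slope is 1.

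If that first-listed test is read as the Aim 2 result, the CI for the effect of VR on pre-sedation anxiety may be wider than the collected data require. Separately, with the covariates and the deciding analysis left open, a choice made after seeing the data would push the error rate above 5%.

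**Working it through.** **The plan's own figure.** Section E sizes Aim 1 only. For 25% against 10%, two-sided 5%, 80% power, the unpooled formula gives (1.960 + 0.842)² × (0.25 × 0.75 + 0.10 × 0.90) / 0.15² = 96.8, so 97 per group. Then 194 / 0.8 = 242.5, so 243. This agrees with "We will require 243 child subjects in the study" and "Allowing for a 20% dropout, we will have 97 subjects in each group". It does not size Aim 2.

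**Patients available for Aim 2.** Both scores are taken before discharge, so dropout at one week does not remove them. Aim 2 may have about 243 / 2, or 121 per arm. That is before exclusions for unexpected admission ("These patients will be excluded and considered screening failures"), which the documents do not size.

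**Assumptions.** The documents give no SD, correlation or effect for m-YPAS. I take normal scores, baseline SD 1, pre-sedation SD k, correlation ρ of 0.3 / 0.5 / 0.7, and a stratum cut at the median.

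**Formulas (variance per patient).**
- Change, as the unadjusted test sees it: V1 = 1 + k² − 2ρk.
- Change, as it really varies between arms under the stratified design: V2 = k²(1 − ρ²) + (kρ − 1)²(1 − 2/π), where 1 − 2/π = 0.363 is the baseline variance left within a median-cut stratum.
- Change, adjusted for baseline and stratum: V3 = k²(1 − ρ²).

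The CI-width ratio, adjusted to unadjusted, is √(V3/V1). The ratio of true sampling SEs is √(V3/V2). The unadjusted SE is overstated by √(V1/V2).

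**Equal SDs (k = 1).**

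| | ρ = 0.3 | ρ = 0.5 | ρ = 0.7 |
|---|---|---|---|
| V1 | 1.40 | 1.00 | 0.60 |
| V2 | 1.088 | 0.841 | 0.543 |
| V3 | 0.91 | 0.75 | 0.51 |
| CI-width ratio | 0.806 | 0.866 | 0.922 |
| True SE ratio | 0.915 | 0.944 | 0.969 |
| SE overstated by a factor of | 1.134 | 1.091 | 1.051 |
| Null rejection, t-test: 2(1 − Φ(1.960 × factor)) | 2.6% | 3.3% | 3.9% |

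Simulation with blocks of 4 within stratum (242 patients, 8,000 trials per setting) agrees:
- Null rejection was 2.7/3.4/4.0% for the t-test and 2.6/3.2/3.9% for the Mann-Whitney, against 5.1% adjusted.
- CI-width ratios were 0.808/0.868/0.924.
- Sampling-variance ratios were 0.836/0.892/0.941. Their square roots are 0.914/0.944/0.970.

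Of the 19/13/8% narrowing, the true fall in sampling SE is therefore about 8 to 9, 5 to 6 and 3%. The rest is removal of an overstated SE. Moving the share of children in the high stratum between 25% and 75% left the width ratios at 0.81/0.87/0.92.

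**Unequal SDs.** At k = 1.25, √(V3/V1) = 0.886/0.945/0.990, or 11/5/1% narrower. At k = 1.5 and ρ = 0.7, V1 = 1.150 and V3 = 1.1475, a ratio of 1.00. The gain vanishes wherever kρ is near 1.

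**Power, for an assumed effect** that gives the unadjusted test 80% nominal power at 97 per arm. At 121 per arm with equal SDs, power is 90.4/89.5/88.7% for the t-test and 97.2/95.0/92.3% adjusted. At k = 1.25 it is 89.3/88.5/88.0% against 94.1/90.9/88.3%.

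**Skewed scores** (lognormal, log-SD 0.5). With an additive effect, Mann-Whitney power is 96.2/95.9/95.8% against 97.1/94.9/92.3% for the untransformed adjusted model, so the rank test wins at ρ = 0.5 and 0.7. With a proportional effect, the Mann-Whitney has 83.6/82.9/82.5%, van Elteren 90.2/88.4/86.7% and the adjusted model on the log scale 97.0/94.7/92.3%.

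**Open choice, no true effect, equal SDs.** Declaring success if either the t-test or one fixed adjusted model is significant gave 5.3 to 5.5% at 242 patients. A separate run at 97 per arm gave 5.4 to 6.1%. Taking the best of five analyses gave 6.5 to 6.9%, but that set includes baseline-only and stratum-only models that the plan does not name.

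**The case against.** The best defence is that nothing here is an error. Analysing change fits the hypothesis in Section B, the unadjusted test is unbiased, and an adjusted model is already planned and might include baseline and stratum. Section E claims no power for Aim 2, so no stated figure fails. All of that stands. What remains is that the text neither names the covariates nor says which analysis leads.

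A reader might infer four stronger things that the documents do not support:
- **The first test ignores the baseline score.** It does not; a change score uses the baseline by subtraction. What is missing is adjustment for it.
- **The first test gives too many false positives.** Used alone it gives fewer than 5%. Only a choice made after seeing the data adds any, and the addition is small.
- **The full 19% is extra precision.** Less than half of it is, and with a larger pre-sedation SD the gain can be nil.
- **Adjustment always wins.** It cost no material power in any normal-score setting run, but with skewed, untransformed scores and an additive effect the plan's own Mann-Whitney can match or beat it. The plan's transformation step therefore matters and should stay.

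**Conclusion.** The point holds as a nearly free improvement to a secondary analysis. The first-listed Aim 2 test does not adjust for the baseline score or the randomisation stratum and is conservative, the adjusted model is unspecified, and no analysis is named as deciding. With normal scores, the CI would be between 0 and about 19% narrower after adjustment; where in that range depends on an SD ratio and a correlation that the documents do not give. The error rate from choosing between the two planned analyses is at most about 6.1% under the settings run. The primary outcome and the stated sample size are untouched, and nothing here shows that Aim 2 is underpowered.

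**What to change.** In Section O, make the already planned adjusted model the main Aim 2 analysis. Specify a linear model (normal distribution, identity link) of m-YPAS change on arm, continuous baseline m-YPAS and the high/low anxiety stratum, and report the adjusted difference with its 95% CI. In this model, using the pre-sedation score as outcome gives the same treatment estimate, so keeping change costs nothing.

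Keep the transformation step. Name in advance a rank test stratified by anxiety group, for example van Elteren, for use if no transformation works. Keep the unadjusted t-test or Mann-Whitney as supportive.

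The cost is a few sentences. Both covariates are already collected, and no patients, visits or measurements are added.
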